Stroke is a leading cause of disability in adults in the US. Currently, IV tPA is the only FDA-approved acute therapy for treatment of ischemic stroke, and is routinely administered to patients in the ED within 4.5 hours of onset of stroke symptoms. After tPA administration in the ED, the patients are routinely monitored in the neurocritical care unit (NCCU) for at least 24 hours for frequent neurological exams and vital sign checks before being eligible to be transferred to a floor bed. While this practice is the current standard of care, there is no rigorous scientific evidence to suggest that all patients require intensive monitoring in the NCCU. In addition, ICU care is costly and ICU resources are scarce. We have recently analyzed the critical care needs and interventions of 153 patients who received IV tPA for acute ischemic stroke at JHH and JHBMC between 2010 and 2013. We found that over 80% of post-tPA patients did not have critical care needs (Faigle et al,

JHMIRB eFormA 01 Version 1 Dated: 11/18/13 manuscript submitted). Furthermore, our data show that 93% of patients without critical care needs by the end of the tPA infusion continue to have an uneventful hospital course with no further critical care needs. The risk of critical care needs for patients presenting with minor stroke symptoms, defined as a presenting NIHSS of 9 or less, was less than 1% if no ICU indication was present by the end of the tPA infusion. We hypothesize that patients who receive IV tPA for acute ischemic stroke in the ED may be safely monitored in a non-ICU environment if they do not have an ICU indication by the end of the tPA infusion and if their presenting NIHSS is below 10.

4. Study Procedures

Design:

The study is a multi-center (2 clinical sites) single arm, open label, pilot clinical trial. The aim is to provide proof-of-concept testing for the safety of non-ICU care in post-tPA patients in acute stroke. The null hypothesis (Ho) is that patients who are monitored in a non-ICU environment post-tPA administration will have ICU needs exceeding 6% of all patients. Six percent was chosen as a cut-off because this is the expected rate of hemorrhage after tPA administration in all stroke patients based on published literature.

The alternative hypothesis (Ha) is that no more than 6% of patients who are monitored in a non-ICU environment post-tPA administration will develop ICU needs.

Treatment Regimen:

IV tPA 0.9mg/kg, maximum of 90mg. Administered by the standard protocol: 10% of the dose by Intravenous bolus injection, followed by infusion of the remainder over 1 hour.

Patients presenting to JHH or JHBMC with signs and symptoms of acute ischemic stroke will undergo evaluation for eligibility of IV tPA in the ED according to the current standard of care: Treatment with IV tPA will be initiated for patients with presumed ischemic stroke presenting within 4.5 hours of symptom onset with a preferred target door to needle time of 60 minutes or less from arrival to the ED. As part of the routine care prior to IV tPA administration all patients will have received the following procedures/tests:

- 1. History, physical examination, and neurological examination including NIHSS.
- 2. EKG, CBC, electrolytes, creatinine and BUN, PT and PTT.
- 3. Two intravenous catheters will be started.
- 4. A non-contrast CT scan of the brain or MRI of the brain per the standard of care protocol at the clinical site.

Patients will receive routine care during the hour of tPA infusion in the ED according to the current standard of care.

Study Interventions:

Patients ages 18-80 are eligible to be enrolled in the study if they present with an NIHSS <10 and if they do not have ICU needs by the end of the tPA infusion. A repeat NIHSS is recorded at the end of the tPA infusion by a member of the stroke team, and the patient or patient representative is approached for enrollment in the study if repeat NIHSS <10 at the end of the tPA infusion. Once the patient has agreed to participate and has signed the consent form, a subject ID number will be assigned. The subject will then be monitored per the non-ICU care protocol (Hopkins protocol) with neurological exams and vital sign checks as specified below. Prior to transfer to the Brain Rescue Unit (BRU) (at JHH site) or Intermediate Medical Care (IMC) (at JHBMC site), subjects will undergo neurological exams and vital sign checks in the ED every 15 minutes during the first hour after tPA completion according to the current standard of care.

Patients will then be moved to the BRU (at JHH) or IMC (at JHBMC) by the end of the first hour after the end of infusion. In order to facilitate bed availability for subjects enrolled in this study, a bed will be made available in an expedited fashion as soon as the decision to administer tPA in a potential subject is made (patients with presumed acute ischemic stroke presenting with NIHSS <10). The admitting neurology resident accompanies the patient to the BRU (at JHH) or IMC (at JHBMC) and gives verbal sign-out to the receiving nurse at the bedside, as it is current standard of

care. Sign-out to the receiving physician (senior resident on the stroke inpatient service at JHH or covering chief resident at JHBMC) will be given at the bedside upon arrival.

The non-ICU protocol (Hopkins protocol) consists of the following schedule for neurological exams and vital sign checks by a stroke-trained nurse: at the time of admission to the unit, then again 1 hour after admission, then every 2 hours for another 8 hours, and then every 4 hours until 24 hours post-tPA are complete. This schedule is slightly more intense monitoring than the current standard of care for non-tPA acute stroke admissions, however, is less intense than NCCU monitoring for post tPA patients.

Subjects will be under the care of the admitting physician that may also be the study investigator. During the first 24 hours all patients will receive a formal NIHSS evaluation for any worsening in neurological exam as determined by the subject's nurse. The NIHSS will be performed by the neurology resident or member of the inpatient team. Nurses will have special training in caring for post tPA patients, and will be familiar with risks and warning signs of tPA related hemorrhage and other complications.

To ensure safety of subjects monitored per non-ICU protocol at JHH, a rapid response (RRT) will be activated if the subject develops any new indication for ICU admission. An RRT includes a prompt evaluation by the on-call NCCU fellow with potential transfer to the NCCU if deemed clinically appropriate. RRT activation for subjects at JHBMC includes discussion with the neurology Chief resident and NCCU fellow for potential transfer to the NCCU if deemed indicated.

Criteria for RRT activation for potential ICU transfer are at the discretion of the treating medical team. In addition to commonly accepted criteria for ICU transfer, worsening of the neurological exam of >3 points on the NIHSS will trigger a STAT head CT and transfer to ICU for intense monitoring if the CT reveals intracerebral hemorrhage or increasing cerebral edema with signs of mass effect. This is based on previously established criteria in the ECASS trial, in which neurologic worsening with an NIHSS >3 was used to evaluate for potential symptomatic intracranial hemorrhage ¹.

Other commonly accepted criteria for need for ICU transfer may include, but may not be limited to, the following:

- uncontrolled hypertension requiring active titration of IV antihypertensives (more than two doses within 30 minutes or frequent dosing (e.g., q 1hr x 3 doses))
- need for vasopressors either for symptomatic systemic hypotension or blood pressure augmentation
- need for invasive hemodynamic monitoring
- uncontrolled hyperglycemia requiring IV Insulin
- respiratory compromise resulting in either initiation of bilevel positive airway pressure (BiPAP) or mechanical ventilation
- arterial bleeding
- management of cerebral edema and increased ICP
- need for neurosurgical intervention such as decompressive craniectomy
- interventional angiography with or without intervention

Once the decision is made to move the patient to the NCCU, subjects will receive routine NCCU care and the subject will be adjudicated as meeting the primary outcome.

After 24 hours (+/- 4 hours) patients will receive either a head CT without contrast or an MRI brain as it is the current standard of care, and will receive an NIHSS by a member of the study team. Thereafter, patients will continue to receive standard care for stroke patients, and will be discharged from the hospital, when medically stable, to the appropriate rehabilitation setting, if any. At the time of discharge all patients will receive a modified Rankin score, and NIHSS.

All patients will return for a follow-up visit at 90 days and will receive a modified Rankin score, and NIHSS. This will be the secondary outcome.

The subject's involvement with this study will end at 90 days after the assessment.

5. Inclusion/Exclusion Criteria

Subject selection:

Both sites for this study are certified stroke centers (JHH and JHBMC). Patients presenting to the ED will be identified upon arrival as acute stroke patients and screened by the ED personnel for time of onset (this is standard procedure). The stroke team will evaluate the patients with a history and neurological exam as well as EKG, laboratory studies and a non-contrast head CT or MRI per the standard of care at the clinical site. Patients with presumed acute ischemic stroke will receive IV tPA in the usual fashion per the current standard of care if presenting to the ED within 4.5 hours of symptoms onset. Every patient receiving IV tPA for presumed acute ischemic stroke will be screened for the presence of inclusion criteria and absence of exclusion criteria, and if found to qualify for the study will be asked to participate after reviewing the details of the study and consent form.

The investigator will explain the clinical trial to the patient or the Legally Authorized Representative (LAR) and will review the consent form, answering any questions. This will be conducted in a private and calm setting as much as it is possible in the ED. The patient or LAR will be given the consent form to review and a copy of signed consent form as well.

Subjects will receive a subject ID that will be a sequential numerical code.

Inclusion criteria:

Subjects will be eligible if the following criteria are met:

- Ability to provide written informed consent (or a LAR available to provide informed consent) and comply with study assessments for the full duration of the study.
- Age 18-80 years

Patient-related considerations (All criteria need to be met):

- Patients to be included will be diagnosed as having an acute ischemic stroke by history and physical exam and receive IV tPA within 4.5 hours of symptom onset according to current guidelines for acute stroke care.
- NIHSS at presentation <10
- Patients do not have ICU needs in the judgment of the treating ED physician or neurologist by the end of the tPA infusion
- NIHSS at the end of tPA infusion <10

Other considerations:

- Some patients will not be able to provide informed consent. In these cases consent will be obtained from the Legally Authorized Representative (LAR).
- Patients that in the judgment of the investigator will not be able to comply with the follow up examinations due to known non-compliance, residence is distant, terminal illness, etc; will not be candidates for inclusion in the trial.

JHMIRB eFormA 01 Version 1 Dated: 11/18/13

Exclusion criteria:

For patients receiving IV tPA according to the current standard of care, the following exclusion criteria apply:

- Age <17 or >80
- ICU need or indication by the end of the tPA infusion
- NIHSS >9 at presentation or at the end of the tPA infusion
- Indication/need for endovascular recanalization therapy

6. Drugs/ Substances/ Devices

No experimental drug will be used in this trial. All patients will receive IV tPA per the standard of care. Tissue plasminogen activator (tPA) is FDA-approved for treatment of acute ischemic stroke, and will be administered at the standard dose for treatment of acute stroke: 0.9mg/kg, 10% IV bolus, and the rest by IV continuous infusion over one hour. Maximum dose is 90mg. tPA Indication and mode of IV tPA administration will occur according to the current standard of care.

7. Study Statistics

Baseline Demographics:

The sample size will be 50 patients, to assess the safety of non-ICU monitoring in post-tPA patients selected according to above criteria. The number of patients receiving IV tPA for acute ischemic stroke at Johns Hopkins Hospital and Johns Hopkins Bayview Medical Center is approximately 75 per year, fairly evenly divided between the 2 locations. Based on our retrospective analysis of 153 patients over 3 years between 2010 and 2012, 85 of 153 patients would have been eligible to participate in this study based on above inclusion and exclusion criteria. Assuming a constant rate of tPA administration per year, this would yield about 27 study subjects per year at JHH and JHBMC, assuming a rate of agreement of 65%. Based on this assessment, this study can be completed in less than two years.

Safety analysis:

Because this study is designed to assess safety, the safety analysis is the same as the primary outcome analysis, which is the assessment of the rate of ICU needs and need for ICU transfer developing in the first 24 hours after IV tPA administration. A DSMB (composed of one member independent of the investigator team) will conduct an analysis of the rate of ICU transfer in the study subjects.

Need for ICU transfer (events) for patients monitored in the non-ICU setting will be evaluated after each subject completes 24 hours of post-tPA monitoring. During the phase of the study in which there are 1-9 subjects, the study will stop at any point there are two events in this group. During the phase of the study in which there are 10-20 subjects, the study will stop at any point if there are three events. During the phase of the study in which there are 20-40 subjects, the study will stop at any point if there are four events. During the phase of the study in which there are 40-50 subjects, the study will stop at any point if there are five events.

Primary endpoint:

 Need for ICU care/interventions (including intracerebral hemorrhage or cerebral edema with mass effect) within the first 24 hours after IV tPA administration will be the primary outcome measure.

Secondary endpoints:

- NIHSS at 24 hours
- NIHSS at discharge
- Modified Rankin Scale at discharge
- NIHSS at 90 days
- Modified Rankin Scale at 90 days
- Mortality at 90 days

Analysis for the secondary endpoints will be done comparing outcomes of study subjects with matched (age, race, NIHSS) controls from our de-identified stroke database of patients receiving IV tPA for acute ischemic stroke under the standard protocol.

Subject discontinuation:

Subjects have a right to withdraw from the study at any time. Subjects that decide to withdraw from the study within the first 24 hours will receive standard of care at the time of withdrawal. No data will be collected on the patient after voluntary withdrawal from the study.

The subject may be withdrawn from the study for any reasons: if it is in the best interest of the subject, intercurrent illness, adverse events, or worsening condition. The IRB, NINDS, the OHRP, the FDA, or other government agencies as part of their duties to ensure that research subjects are protected, may request the withdrawal of a subject because of protocol violations, administrative reasons, or any other valid and ethical reasons.

8. Risks

Risks potentially associated with non-ICU monitoring may result from delayed recognition of medical or neurological deterioration, with limited capability of rapid intervention in a non-ICU setting.

Most complications related to IV tPA administration are neurological deterioration secondary to intracerebral hemorrhage. In our retrospective analysis, almost all patients who developed ICU needs after IV tPA developed such needs during the tPA infusion. In the present study, subjects are being monitored in the ED with frequent neurological examinations and vital sign checks during the tPA infusion, and for up to an additional hour, as it is the current standard of care. In the non-ICU setting, a stroke trained nurse will assess the patient upon admission to the floor, and then again after 1 hour, thereby ensuring adequate frequency of examinations and vital sign checks in the most critical post-tPA period. Thereafter, neurological exams and vital sign checks will be less frequent, every 2 hours for 8 hours, and then every 4 hours until 24 hours post-tPA are complete. Nurses will have special training in caring for post tPA patients, and will be familiar with risks and warning signs of tPA related hemorrhage and other complications. Per protocol, any change in neurological exam will result in a formal evaluation by the covering neurology resident or member of the inpatient team who will obtain an NIHSS. At JHH an RRT (with evaluation by the on-call NCCU fellow) for potential transfer to the NCCU will be activated for any increase in NIHSS > 3 points from baseline (post-tPA NIHSS). Similarly, any medical deterioration requiring ICU care in the judgment of the provider will result in activation of an RRT with potential transfer to the NCCU. Similarly, at JHBMC RRT activation for subjects will follow the same criteria, and includes discussion with the neurology Chief resident and NCCU fellow for potential transfer to the NCCU if deemed indicated.

Safety assessments will consist of monitoring and reporting adverse events (AE) and serious adverse events (SAE) that are considered to be related to non-ICU monitoring, all events of death, and any study specific issue of concern.

JHMIRB eFormA 01 Version 1 Dated: 11/18/13 An AE is defined as any unfavorable and unintended sign, symptom, or disease temporally associated with non-ICU monitoring.

This includes the following:

- Any event or change in condition within the first 24 hours after tPA administration that requires ICU care or ICU intervention.
- AEs not previously observed in the subject that emerge during the protocol-specified AE reporting period, including signs or symptoms associated with ischemic stroke that were not present prior to the AE reporting period.
- Complications that occur as a result of protocol-mandated interventions (e.g., invasive procedures such as cardiac catheterizations).
- Preexisting medical conditions (other than the condition being studied) judged by the investigator to have worsened in severity or frequency or changed in character during the protocol-specified AE reporting period.

An AE should be classified as an SAE if:

- It results in death
- It is life threatening
- It requires prolonged hospitalization
- It results in persistent or significant disability/incapacity

All AEs and SAEs whether volunteered by the subject, discovered by study personnel during questioning, or detected through physical examination, laboratory test, or other means will be reported appropriately.

9. Benefits

By potentially avoiding an unnecessary ICU stay, participants may benefit from an expedited stroke work-up and reduced length of hospital stay. Admission directly to the floor would result in less frequent interruptions for neurological exams and vital sign checks, which may improve quality of sleep. In addition, bypassing ICU care would reduce the number of hand-offs between different providers and provider teams, and thereby reduce the chance for medical errors. Avoiding unnecessary ICU admission would greatly reduce cost for stroke admissions and reduce the financial burden on society associated with acute stroke care.

10. Payment and Remuneration

There will be no payment to participants.

11. Costs

There are no anticipated additional costs to participants.

12. References

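### Does the forecast of 27 subjects per year conflict with the sponsor's own series of 153 tPA patients over 3 years?

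*Combined protocol and SAP*

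**What the plan says.** The forecast is in section 7, Study Statistics, under Baseline Demographics. The target is given first: "The sample size will be 50 patients". The combined tPA volume at the two hospitals "is approximately 75 per year, fairly evenly divided between the 2 locations". The eligible fraction comes from earlier data: "Based on our retrospective analysis of 153 patients over 3 years between 2010 and 2012", of which "85 of 153 patients would have been eligible to participate in this study based on above inclusion and exclusion criteria". The paragraph then makes its rate assumption ("Assuming a constant rate of tPA administration per year"), states the result ("this would yield about 27 study subjects per year at JHH and JHBMC, assuming a rate of agreement of 65" per cent), and concludes that "this study can be completed in less than two years".

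Section 3, Background, describes the same series with a different end year: "153 patients who received IV tPA for acute ischemic stroke at JHH and JHBMC between 2010 and 2013".

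**The concern.** Two annual volumes appear side by side. One is stated, at about 75. The other is implied: 153 patients over 3 years is 51 per year, and sections 1 and 3 place that series at the same two hospitals. The text mentions no growth in volume and does not say that the 153 are a subset. The assumption of a constant rate seems to rule growth out. If the series is the better guide, the forecast is about one third too high and enrolment takes about 2.7 years. The differing end years (2012 and 2013) add doubt, because a longer window would lower the implied rate further.

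A statistical consequence could be argued as well. If the trial closed at two years under the slower rate, it would have about 37 patients. Taking a one-sided 5% level against the 6% threshold in section 4 (Design), even zero events in 37 would not exclude 6%.

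**Working it through.** **Inputs**, all from section 7, Baseline Demographics:

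- target: 50
- stated volume: about 75 per year
- series: 153 patients over 3 years
- eligible: 85 of 153
- agreement: 65%

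**Formulas.** Accrual per year = annual tPA volume × (85/153) × 0.65. Years to enrol = 50 / accrual.

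**The plan's own figure.**

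- 75 × 0.5556 = 41.7 eligible per year
- 41.7 × 0.65 = 27.1 enrolled per year
- 50 / 27.08 = 1.85 years (22.2 months)

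The stated yield of 27 and the stated duration both reproduce as an enrolment forecast, so the multiplication is sound.

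**The same formula with the series rate.**

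- 153 / 3 = 51 per year
- 51 × 0.5556 = 28.3 eligible per year
- 28.3 × 0.65 = 18.4 enrolled per year
- 50 / 18.42 = 2.71 years (32.6 months)

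The difference is 32.6 − 22.2 = 10.4 months. In relative terms, accrual is (27.08 − 18.42) / 27.08 = 32% slower.

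The figure 85 / 3 = 28.3 is close to 27, but it leaves out the 65% agreement that the text says was applied. Once that is applied, only 75 per year gives 27.

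**Size of the gap.** Three years at 75 would be 225 patients, 1.47 times the 153 in the series. Enrolling 50 in exactly two years means 25 per year. That needs 25 / (0.5556 × 0.65) = 69 tPA patients per year, or, at 51 per year, agreement of 25 / 28.3 = 88%.

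**The series dates.** Four years would give 153 / 4 = 38.3 per year, 13.8 enrolled per year and 3.6 years. That case can be set aside. Section 7 gives 3 years, the protocol is dated 18 November 2013, and section 3 says the manuscript was already submitted, so four full calendar years could not have been analysed. A span of 3.5 years would give 43.7 per year, 15.8 enrolled per year and 3.2 years, but it also departs from the stated 3 years. A span from 2010 to 2013 can itself be three years long.

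**The inferential argument.** Two years at 18.4 per year gives 36.8, or about 37 patients. With zero events in 37, the one-sided 95% upper limit is 1 − 0.05^(1/37) = 7.8%. With zero events, 6% is first excluded at n = 49 (0.94^48 = 0.051; 0.94^49 = 0.048). These sums are right, but they need two premises that the plan does not contain: closure at two years and a stated 5% level.

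**What ends enrolment.** Section 7 sets 50 patients. Its Safety analysis adds early stopping on event counts only (two, three, four or five events, according to the number enrolled). No calendar limit appears anywhere.

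**The case for a change.** The best case for acting is that the conflict can be verified in a single paragraph, moves the forecast by about a third, and would cost one sentence to resolve. This paragraph is also the only support given for accrual, and the Abstract names feasibility as an aim. Even if 75 is accepted, adding the 90-day follow-up (about 0.25 year) to 1.85 years gives about 2.1 years, so the claim of under two years holds for enrolment only.

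Some of this stands. The gap between 75 and 51 is real and unexplained, the two end years differ, and the duration claim has to be read as enrolment.

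The rest is weaker:

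- The 51 is an inference. It equals tPA volume only if the 153 were every treated patient at both hospitals, and the documents never say that the series was complete or consecutive. A subset with usable records, or a higher present volume, would fit the text equally well, though neither is stated.
- The constant-rate assumption can be read as holding the 75 just quoted steady through the trial.
- Feasibility in the Abstract means whether these patients can safely be monitored outside an ICU. Accrual speed is not among the objectives in section 2.

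**Conclusion.** No change follows, because a change would gain nothing for the trial's conduct or conclusions. The forecast is arithmetically correct on its stated volume: 27.1 per year and 1.85 years of enrolment. The alternative of 18.4 per year and 2.7 years is conditional on the 153 patients being a complete count over exactly 3 years, which the documents do not establish. A fair reading is a range of 18 to 27 per year, or 1.8 to 2.7 years of enrolment.

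At the slow end the trial lasts about 10 months longer and still enrols 50. The sample size, the 6% threshold, the stopping rule, the endpoint and the analysis are the same in both cases. The argument from 0 of 37 depends on a two-year closure and a significance level that the plan does not state, so it does not make a planning forecast into an inferential problem. The 2012 and 2013 end years are a slip in wording at most.

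### The DSMB member's stated task and the stopping limits cover only 24-hour ICU need, so later deaths and disabling SAEs that the trial already records are not put before that member during enrolment

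*Combined protocol and SAP*

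**What the plan says.** Section 7, Safety analysis, states that "the safety analysis is the same as the primary outcome analysis". That outcome is ICU need or ICU transfer during the first day after tPA. The DSMB, a single member independent of the investigators, is given one task: the member "will conduct an analysis of the rate of ICU transfer in the study subjects". No other task is listed.

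The stopping limits follow under the same heading. The counted event is need for ICU transfer, which "will be evaluated after each subject completes 24 hours of post-tPA monitoring". The study stops at two events while there are 1-9 subjects, three at 10-20, four at 20-40 and five at 40-50. The primary endpoint is "Need for ICU care/interventions (including intracerebral hemorrhage or cerebral edema with mass effect) within the first 24 hours after IV tPA administration".

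Later harm is handled elsewhere. Section 8 (Risks) has the team monitor and report AEs and SAEs "considered to be related to non-ICU monitoring, all events of death, and any study specific issue of concern". Its SAE list includes death and lasting disability. It ends by saying that all AEs and SAEs will be reported suitably, and names no recipient. Section 7 lists mortality, mRS and NIHSS at 90 days as secondary endpoints, compared with matched database controls. No interim look at these is described.

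**The concern.** Section 8 names the hazard of the intervention: "Risks potentially associated with non-ICU monitoring may result from delayed recognition of medical or neurological deterioration". Some consequences of late recognition, such as death or lasting disability, may become apparent only after the first day. A count that closes for each subject at 24 hours is not built to show them.

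The trial collects this information anyway. As written, though, the DSMB member is not asked to look at it, and no stopping limit responds to it. If a few subjects did badly after the window closed, further subjects could be enrolled under the lighter monitoring schedule before the member had considered those cases.

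**Working it through.** **1. What reaches the DSMB member, by event type.**

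| Event | Counted by the stopping limits or in the stated remit? | Recorded elsewhere? |
|---|---|---|
| ICU need within 24 h, including hemorrhage or edema with mass effect | Yes (section 7) | Yes (section 8, AE list) |
| Fatal hemorrhage within 24 h, no transfer made | Can reasonably be counted, since the endpoint is need for ICU care | Yes |
| Death after 24 h, to day 90 | No | Yes (section 8; 90-day mortality in section 7) |
| Disabling SAE recognised after 24 h | No | Yes as an SAE (section 8), though one judged unrelated is less clearly covered; mRS and NIHSS at discharge and day 90 |

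The last two rows are the gap.

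**2. How narrow it is.** Section 4 (Study Interventions) sets a scan and a study-team NIHSS at 24 +/- 4 hours:

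- earliest: 24 - 4 = hour 20
- latest: 24 + 4 = hour 28

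Much of what the 24-hour count might miss should therefore be seen within about four hours of the window closing. Seeing it is not the same as sending it to the DSMB member. A finding at hours 24-28 comes after the point at which section 7 evaluates the subject.

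**3. Would review still be in time?** Inputs from section 7: about 75 tPA patients a year, 85 of 153 eligible, 65% agreement, 50 subjects.

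- The plan's own accrual figure: 75 x 85/153 x 0.65 = 27.1 a year. The plan says about 27, so it reproduces.
- Duration: 50/27 = 1.85 years, about 22 months.
- Enrolled during one subject's 90 days: 27 x 90/365 = 6.7, rounded up to 7.
- Enrolled after day 90 of subject k: max(0, 50 - k - 7). The sum over k = 1 to 50 is 42 + 41 + ... + 1 = 903, and 903/50 = 18.1.
- Slower case, using 153 patients in 3 years (51 a year): 51 x 85/153 x 0.65 = 18.4 a year. Then 18.4 x 90/365 = 4.5, rounded up to 5. The sum is 44 + 43 + ... + 1 = 990, and 990/50 = 19.8.

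On average, then, about 18 to 20 subjects enrol after a given subject's day 90, and more after an event learned of sooner. This assumes steady accrual to 50. It shows timing only. It is not multiplied by any event probability and is not an estimate of benefit.

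**4. Reviewer load (assumed rates).** If 2% to 20% of subjects had a reportable event, there would be 50 x 0.02 = 1 to 50 x 0.20 = 10 reports. At the upper end that is one every 22/10 = 2.2 months. Each further 10% of subjects would add 50 x 0.10 = 5 reports.

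**5. Cost of a pause (assumed length).** A 7-day pause misses 7 x 27/365 = 0.52 enrolments. Two such pauses miss 1.04.

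**The case against.** The strongest reply is that this is a 50-subject pilot of an intervention that ends at 24 hours, so a 24-hour safety measure is the natural one. The endpoint counts need for ICU care rather than completed transfers, and it includes hemorrhage and edema with mass effect. A scan follows by hour 28. Ninety-day mortality and function are compared with matched controls, a comparator that a reviewer of single late deaths in a one-arm stroke cohort would lack. All of this stands, and it is why the gap is small. It does not close the gap, because the matched comparison has no stated interim look.

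A second reply is that the argument rests on silence. Section 7 does not say that the member may see nothing else, and section 8 excludes no recipient. That is fair. A reader might infer that late deaths would go unreported or receive no independent review at all. The documents do not support that: section 8 requires all deaths to be reported, and the text does not rule out other oversight. What the text shows is only that the member's stated task does not include these events.

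A third reply is that no study contact is scheduled between discharge and day 90, so some events will be learned of late. This also stands. Forwarding can only be prompt from the time the team learns of an event.

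Finally, section 8 mentions an AE reporting period without giving its length, and its sentences differ on whether reporting depends on relatedness. These are missing details of drafting, and the point does not rest on them.

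**Conclusion.** The point holds as a minor one. The stated remit and the stopping limits are confined to ICU need or transfer in the first 24 hours. Deaths and disabling SAEs recognised later are recorded but not put before the DSMB member while enrolment continues.

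The expected number of such events cannot be derived, because the documents give no rate for late-recognised harm. A reader might take the critical-care risk of under 1% in section 3 (Background) as a ceiling, giving fewer than 50 x 0.01 = 0.5 subjects. That does not follow. The figure concerns critical care needs in a retrospective cohort under standard care. A death without ICU care, or disability emerging by day 90, need not fall within that group.

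Nor does the point imply that the stopping limits are wrong or should count late events. Many late deaths or disabilities may reflect the index stroke, and adding them to the count would change what the limits measure.

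The conclusion assumes that no separate DSMB charter widens the remit. The documents mention none.

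**What to change.** In section 7, Safety analysis, add to the existing DSMB member's remit all deaths through day 90 and all SAEs with persistent or significant disability. Have them forwarded when the study team learns of them, with no filter for relatedness or for the index stroke, since either would bring back an attribution judgement before the independent look. State that the member may recommend a pause in enrolment after review, with no automatic hold. Leave the 2/3/4/5 limits unchanged, and add no contacts or visits.

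The cost is a short wording change and a few extra reports for one reviewer: 1 to 10 under the assumed 2% to 20%, possibly more because nothing is filtered out. Many will reflect the index stroke rather than the monitoring. There may be a short discretionary pause. With 0 to 2 pauses of 7 days (assumed), 0 to about 1 enrolment is missed. The stopping limits keep their operating characteristics, apart from any pause the member recommends.
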